4.10.3 Secondary Cardiac Variables

4.10.3.1 Central tendency analysis

The holter extracted ECG parameters will be summarized separately using descriptive statistics, on raw values and changes from baseline (Δ). Descriptive statistics will be computed per treatment group, day, dose level and time points.

Mean changes with their 95% CI will be plotted over time per treatment.

For all parameters, the changes from baseline (Δ) will be analysed using an analysis of variance model (ANOVA) including treatment, time and their interaction as main factors and structuring the residual matrix in order to account for the repeated measurement pattern of the data. The baseline value (centered on population mean) will be considered as covariate. This analysis will be performed by day in order to evaluate the therapeutic setmelanotide dose at day 10 and the supra-therapeutic setmelanotide dose at day 16.

At each time point, estimates (LSmeans) of treatment effects and differences between setmelanotide dose levels and placebo ($\Delta\Delta$) will be obtained with their 2-sided 90% CIs.

$\Delta\Delta$ Estimates with their 90% CI will be plotted over time per day/dose level.

For moxifloxacin vs. placebo evaluations, the changes from baseline will be analysed per time point, for each parameter separately, using analysis of variance model including terms for treatment and considering the subject as random effect. The analysis will be performed by day (day 10 vs. day 16).

At each time point, estimates (LSmeans) of treatment effects and differences between moxifloxacin and placebo ($\Delta\Delta$) will be obtained with their 2-sided 90% CIs.

$\Delta\Delta$ Estimates with their 90% CI will be plotted over time per day.

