3.1 Overall Study Design and Plan

This is a double-blind, randomized, placebo- and positive-controlled, parallel group, 3-arm study to assess the potential for therapeutic and supratherapeutic concentrations of SC setmelanotide administered as IMCIVREE to affect the QTcF interval compared with placebo. Approximately 72 healthy subjects aged 18 to 50 years of age, inclusive, are planned to be enrolled in the United States. Subjects will be enrolled into 1 of 3 groups as follows:

- Group 1: SC setmelanotide; oral placebo on Days 10 and 16
- Group 2: SC placebo; oral moxifloxacin on Day 10 and oral placebo on Day 16
- Group 3: SC placebo; oral placebo on Day 10 and oral moxifloxacin on Day 16.

The study design is presented in [Figure 3-1](#).

Figure 3-1 Study Design Schematic

Upon providing informed consent, subjects will enter a 28-day Screening period, during which they will be assessed for eligibility and complete all screening procedures as described in the Schedule of Assessments (SoA) ([Table 6-1](#)).

Following the Screening period, eligible subjects will check-in to the Clinical Research Unit (CRU) on the morning of Day -2. Subjects will be randomized 1:1:1 into Group 1, 2, or 3 and will be fasted overnight (for at least 10 hours). On the morning of Day -1 following a standard breakfast, subjects will undergo 24-hour continuous ECG Holter monitoring beginning 30 minutes after the meal (at the time of anticipated dosing on Days 10 and 16). Baseline assessments ([Table 6-1](#)) will occur on Day -1.

On the morning of Day 1, subjects will receive SC setmelanotide 2 mg (Group 1) or SC placebo (Groups 2 and 3) in a double-blinded fashion.

From Days 2 to 16 following a standardized breakfast, subjects will continue receiving SC setmelanotide (3 mg QD from Days 8 to 10; 5 mg QD from Days 11 to 13; 7 mg QD from Days 14 to 16) or SC placebo according to their assigned group. On Days 10 and 16, oral placebo or oral moxifloxacin 400 mg will be administered with the SC dose according to the assigned dose group. Continuous Holter ECGs and PK sampling will be conducted on Days 10 and 16 pre-dose and for up to 24 hours post-dose according to the SoA ([Table 6-1](#)). All treatments administered in the CRU will be double-blinded and will be given at the same time every day (approximately 30 minutes after the start of breakfast).

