3.2 Endpoints and Associated Variables

Triplicate values for HR (bpm), RR (msec), PR (msec), QRS (msec) and QT (msec) will be extracted by the ECG core lab at Day -1 and on Days 10 and 16 at the following timepoints: pre-dose and 0.5, 1, 1.5, 2, 2.5, 3, 4, 5, 6, 7, 8, 9, 10, 12, 16, and 24 hours post-dose. The Day -1 extractions will begin at 7:30 AM (the time of anticipated dosing on Days 10 and 16).

Heart rate corrected QT intervals will be derived from the QT and RR intervals for each replicate at each time point:

- o Fridericia's cube-root corrected QT⁽¹⁾: QTcF (msec) = QT (msec) / (RR(msec)/1000)^{1/3}
- o Bazett's square-root corrected QT⁽²⁾: QTcB (msec) = QT (msec) / (RR(msec)/1000)^{1/2}

At each time point, the triplicate values will be averaged in order to obtain 1 single value per subject and time point. The averaged values will be rounded to the nearest integer. Changes from baseline and percent changes from baseline will be computed as:

- o $\Delta Y_{i,k,j} = Y_{i,k,j} - Y_{i,D-1,j}$
- o $\Delta_{rel} Y_{i,k,j}(\%) = 100 \times (Y_{i,k,j} - Y_{i,D-1,j}) / Y_{i,D-1,j}$
- o With i=Subject, j=time, k=Day

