4.2.4 Baseline

Baseline is defined as the last non-missing measurement recorded before first dose of the study drug administration for res.

Time-matched Measurements:

For Continuous 12-lead ECG using Holter's readings for Cardiac endpoints, baseline is defined as the time-matched measurements on Day -1.

No imputation will be done for missing baseline value for derivation of change from baseline or summary tables and shift tables.

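### The by-time-point moxifloxacin model carries a redundant subject random effect and leaves out the baseline covariate used in the sister models: a modest precision and specification issue in a secondary analysis

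*SAP*

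**What the plan says.** SAP 4.10.3.1 has two models for change from baseline.

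- **Setmelanotide v placebo.** All time points of a day enter one model with treatment, time and their interaction, "structuring the residual matrix in order to account for the repeated measurement pattern of the data". It adjusts for baseline: "The baseline value (centered on population mean) will be considered as covariate".
- **Moxifloxacin v placebo.** Here "the changes from baseline will be analysed per time point, for each parameter separately". Each of these fits is specified as one "using analysis of variance model including terms for treatment and considering the subject as random effect". The fits are also split by day: "The analysis will be performed by day (day 10 vs. day 16"). No baseline term is named, and no reason is given for the difference.

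Three other places fix the number of records in each moxifloxacin fit.

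- SAP 3.2: "the triplicate values will be averaged in order to obtain 1 single value per subject and time point".
- SAP 4.2.4, for the Holter endpoints: "baseline is defined as the time-matched measurements on Day -1". Each subject therefore has one change value per day and time point.
- SAP 3.1: each subject in the two moxifloxacin groups takes one oral treatment per Holter day. For example, "Group 2: SC placebo; oral moxifloxacin on Day 10 and oral placebo on Day 16"; Group 3 has the reverse order.

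**The concern.** A subject random effect needs at least two records from some subjects. Here each subject has one, so the stated model contains a variance component that the data cannot estimate. The term would make sense if both days entered one model, because Protocol 5.3 says that Groups 2 and 3 receive both oral treatments to act as their own controls. The by-day split removes that pairing, so the two instructions do not fit together.

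The missing covariate is a separate matter. Eq. 1 in SAP 4.10.2.1.3 contains centred baseline, and SAP 4.10.3.3 carries that method over to the moxifloxacin concentration-QTc model. The by-time-point moxifloxacin model is therefore the only treatment-effect model for change from baseline in SAP 4.10 without it.

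At stake is the precision of a named secondary endpoint, the placebo-corrected change after moxifloxacin (SAP 3.2.2). Table 4-1 also uses the placebo-corrected time course as a check that its largest value agrees with the concentration-QTc prediction, and SAP 4.10.3.3 applies that check to moxifloxacin.

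**Working it through.** **Inputs.** 20 moxifloxacin and 20 placebo evaluable subjects on each day (SAP 4.13). SD of the QTcF change 8 msec in both arms (Protocol 11.1.2). Two-sided 90% intervals (SAP 4.10.3.1). The correlation rho between the Day -1 and on-treatment value at a time point is not in the documents, so I assume a range.

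**The plan's own figure.** No precision or power is stated for this model. The nearest figure is the power of at least 81% per day in SAP 4.13, which belongs to the concentration-QTc analysis. A two-sample t-test at 20 v 20, SD 8 and a margin of 10 − 5 = 5 msec gives 61.6%. That mismatch is a separate matter and nothing below depends on it.

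**Step 1: can the random effect be estimated?** With one record per subject, the covariance matrix is (subject variance + residual variance) × identity. Only the sum enters the likelihood. In a simulated 20 v 20 data set, I split the same total variance in different ways:

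| Share given to subject | REML log-likelihood (up to a constant) | Difference, msec | SE, msec |
|---|---|---|---|
| 0% | −99.2018 | 10.555 | 2.412 |
| 25% | −99.2018 | 10.555 | 2.412 |
| 50% | −99.2018 | 10.555 | 2.412 |
| 75% | −99.2018 | 10.555 | 2.412 |
| 99% | −99.2018 | 10.555 | 2.412 |

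The split is not identifiable. The difference and its SE are those of a plain two-group ANOVA. What stays open is the t multiplier: the plain ANOVA has 40 − 2 = 38 degrees of freedom, while a rule that counts the subject columns finds rank 40 on 40 records and nothing left for residual. The SAP names no degrees-of-freedom method.

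**Step 2: half-width as planned, with 38 degrees of freedom.** SE = 8 × sqrt(2/20) = 2.53. Half-width = 1.686 × 2.53 = 4.27 msec.

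**Step 3: half-width with the baseline covariate.** Assume equal variance sigma² at baseline and on treatment.

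- The change has variance 2·sigma²·(1 − rho).
- After adjustment for baseline the residual variance is sigma²·(1 − rho²).
- The ratio is (1 + rho)/2.
- Chance imbalance in the covariate costs a factor 1 + 1/(40 − 4) = 1 + 1/36.
- Half-width = t(0.95, 37) × 2.53 × sqrt[(1 + rho)/2 × (1 + 1/36)], with t(0.95, 37) = 1.687.

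| rho (assumed) | SE ratio | Half-width, msec | Simulated mean half-width |
|---|---|---|---|
| 0.6 | 0.907 | 3.87 | not run |
| 0.7 | 0.935 | 3.99 | 3.96 |
| 0.8 | 0.962 | 4.11 | 4.08 |
| 0.9 | 0.988 | 4.22 | 4.19 |
| 0.95 | 1.001 | 4.27 | 4.24 |

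The simulation used 20,000 runs per rho. Its unadjusted mean half-width was about 4.24, so it agrees with the formula on the relative gain.

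**Step 4: the alternative with both days in one model.** For 40 subjects with both days, half-width ≈ 1.686 × 8 × sqrt[2(1 − r)/40], where r is the correlation between a subject's two changes. This gives 3.02 msec at r = 0 and 2.13 msec at r = 0.5. The documents do not give r. Equal variances and equal correlations across the three Holter days would make it 0.5: both changes subtract the same Day -1 value, so their covariance is sigma²·(1 − rho), half the variance of each. This is one estimate over both days, so it is not like for like with a per-day interval.

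**The case against.** **Stronger readings that do not hold.**

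- A reader might infer that the moxifloxacin intervals are unreliable because the model is not identifiable, or that no degrees of freedom remain. Step 1 does not support that. Only the split between two variances that nobody reports is undetermined. The count that leaves no residual degrees of freedom treats subject as a fixed effect. What remains is the unnamed degrees-of-freedom convention, and the documents do not allow its effect to be sized.
- A reader might infer that the random effect costs precision. It does not; the loss comes only from the missing covariate.
- A reader might use (1 + rho)/2 alone and put the gain at 25% to 5% more subjects for rho 0.6 to 0.9 (1/0.80 and 1/0.95). With the factor 1 + 1/36 it is about 22% to 2%. Rho is also tied to the spread of QTcF: with the SD of change fixed at 8, rho = 1 − 32/sigma², so rho 0.6 needs sigma of about 8.9 msec and rho 0.9 about 17.9. The documents give no sigma.

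**What can fairly be said for the plan.** Groups are randomised, so an unadjusted comparison of changes is unbiased; the covariate is a matter of efficiency and consistency. SAP 4.10.3.1 attaches no threshold or test to this analysis, and Protocol 11.3.1 promised only descriptive summaries by time point. Assay sensitivity is decided by the concentration-QTc model in SAP 4.10.3.3, which already has centred baseline. One could also hold that the covariate carries over from the preceding paragraph, but the moxifloxacin sentence lists its own terms and baseline is not among them.

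All of this limits the weight of the point. It does not explain a random effect with one record per subject, or why one of the models leaves baseline out.

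**Conclusion.** The point holds as a specification and precision improvement to a secondary analysis. Two facts are certain from the text: each fit has one record per subject, which makes the random effect redundant, and no baseline covariate is named. The estimate and its SE are unaffected by the first.

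The second costs about 9% of the half-width at rho 0.6, 4% at 0.8, 1% at 0.9 and nothing near 0.95. These sizes rest on 20 v 20, SD 8, equal variances and an assumed rho. No bias follows, and neither the primary conclusion nor the assay-sensitivity decision changes. It is worth correcting because the covariate already exists wherever a change can be computed.

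**What to change.** Reword the moxifloxacin paragraph of SAP 4.10.3.1 in one of two ways.

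1. **Keep the by-day analysis.** For each parameter, time point and day, fit change = treatment + centred Day -1 value at that time point, with no subject random effect. The degrees of freedom are then unambiguous: 37 at 20 v 20.
2. **Use the within-subject comparison in Protocol 5.3.** At each time point, analyse both days in one model with treatment, period, sequence and random subject, keep the baseline covariate, and name the degrees-of-freedom method. The random effect is then estimable. The Day -1 value is common to both days and cancels from a completer's within-subject difference, so the gain comes mainly from the pairing.

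The choice has a trade-off: option 1 gives separate Day 10 and Day 16 time courses but forgoes the pairing; option 2 gives a more precise single time course. SAP 4.10.3.3 justifies its own by-day split by a differing moxifloxacin baseline, whereas SAP 4.2.4 sets Day -1 for all Holter changes. A sponsor choosing option 2 should reconcile these.

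The cost is SAP wording and a small programming change before unblinding. No new data are needed. Option 1 spends one degree of freedom and gains nothing if rho is near 0.95.

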4.10.3.2 Categorical analyses

For the analyses described in this section, a treatment-emergent abnormality/finding will be defined as any abnormality/finding not already reported on any of the ECGs collected before the administration.

The analysis will be performed for setmelanotide and moxifloxacin evaluation.

4.10.3.2.1 Incidence of abnormal values

Average of the replicates extracted at each time point will be considered for this categorical analysis consisting on the display of the number and percentage of subjects by day and treatment group presenting at least one treatment emergent abnormality according to pre-defined thresholds presented in [Table 4-2](#).

Table 4-2 Thresholds for abnormalities and corresponding flags for listings

Criteria	Flag for listings
Actual values	
HR<40 beats/min	L
HR>120 beats/min	H
PR>220 msec	H
QRS>120 msec	H
450<QTc≤480 msec	B
480<QTc≤500 msec	H
QTc>500 msec	P
Changes from baseline	
HR relative change >25%	I
PR relative change >25%	I
QRS relative change >25%	I
30<QTc increase≤60 msec	I
QTc increase>60 msec	I+

Flagging system will be used in listings to identify values above thresholds, also not necessarily related to clinically significant events, the flags can be interpreted as follows:

L: Low value - B: Borderline value - H: High value - P: Prolonged value

I: Noticeable increase from baseline - I+: marked increase from baseline

QTc denotes all correction methods

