3.1.2. Setmelanotide

Setmelanotide (also known as RM-493) is a synthetic, cyclic octapeptide (8-amino acid-containing peptide) that functions as a potent MC4R agonist. Setmelanotide is an 8-amino acid, cyclic peptide that binds with high affinity (inhibitory constant $[K_i] = 2.1$ nM) to the human MC4R and is efficient in activating MC4R (50% effective concentration $[EC_{50}] = 0.27$ nM). Setmelanotide is indicated for chronic weight management in adult and pediatric patients 6 years of age and older with obesity due to POMC, PCSK1, or LEPR deficiency confirmed by genetic testing demonstrating variants in *POMC*, *PCSK1*, or *LEPR* genes that are interpreted as pathogenic, likely pathogenic, or of uncertain significance ([IMCIVREE \(setmelanotide\) Prescribing Information 2020](#)).

Setmelanotide was evaluated extensively in nonclinical studies for cardiovascular parameters, primarily because of the potential concern for effects on blood pressure (BP) and heart rate (HR). The IC_{50} for the effect of setmelanotide on human ether-à-go-go-related gene (hERG) potassium current was estimated to be greater than 300 μ g/mL, the maximum concentration tested. In addition, an extensive, multi-day cardiovascular telemetry study with setmelanotide administered by subcutaneous (SC) continuous infusion was performed in cynomolgus monkeys. No setmelanotide-related effects were noted on the electrocardiogram (ECG) parameters (PR, QRS, QT, and QTc intervals) following the administration at doses of 2.5, 12, and 25 mg/kg/day. In both these studies, there were extremely large exposure/concentration margins to the approximate Cmax of the maximum therapeutic 3 mg SC injection dose (~40.0 ng/mL) and the anticipated Cmax of the supratherapeutic 7 mg SC injection dose (~93.3 ng/mL, assuming dose proportionality).

QTc evaluations were additionally conducted in 3 initial Phase 1 and Phase 2 clinical studies, as well as in 57 patients with monogenic obesity in 3 Phase 2 and Phase 3 studies. Mean and median data for QTcF demonstrate no effect of setmelanotide on QTc interval at doses up to 3 mg QD.

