6.2. Subject Exclusion Criteria

Subjects meeting any of the following criteria are not eligible for study participation:

1. Subject has sustained systolic blood pressure (SBP) >150 mmHg or <90 mmHg or a diastolic blood pressure (DBP) >100 mmHg or <60 mmHg in the supine position at Screening.
2. Subject has supine pulse rate of <45 beats per minute (bpm) or >100 bpm.
3. Subject has abnormal screening ECG indicating a second- or third-degree atrioventricular block, or one or more of the following: QRS >110 msec, QTcF >450 msec for males and >470 msec for females, PR interval >200 msec.
4. Subject has a history of risk factors for Torsades de Pointes (TdP), including unexplained syncope, diagnosis or family history of Brugada syndrome or long QT syndrome, heart

failure, myocardial infarction, angina, or clinically significant abnormal laboratory assessments including hypokalemia, hypercalcemia, or hypomagnesaemia.

5. Glomerular filtration rate (GFR) <60 mL/min at Screening.
6. Subject has significant dermatologic findings relating to melanoma or pre-melanoma skin lesions (excluding non-invasive basal or squamous cell lesion), determined as part of comprehensive skin evaluation performed by the Investigator during Screening. If any concerning lesions are identified during Screening, the subject should be referred to a dermatologist for evaluation prior to enrollment. If the pre-treatment evaluation results are of significant concern, the subject is not eligible for study participation.
7. Subject has history or close family history (parents or siblings) of melanoma or subject history of ocular-cutaneous albinism.
8. Subject has significant history or clinical manifestation of any metabolic, allergic, dermatological, hepatic, renal, hematological, pulmonary, cardiovascular, gastrointestinal, neurological, or psychiatric disorder (as determined by the Investigator).
9. Subject has suicidal ideation of type 4 or 5 on the C-SSRS at Screening, a history of a suicide attempt in their lifetime, or any suicidal behavior in the last month.
10. Subject has participated in any clinical study with an investigational drug/device within 30 days (or 5 half-lives) prior to the first day of dosing.
11. Subject was previously enrolled in a clinical study involving setmelanotide or any previous exposure to setmelanotide.
12. Subject has inability to comply with QD injection regimen.
13. Female subjects who are breastfeeding or nursing.

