11.3.1. Cardiodynamic ECG Assessment

The primary analysis will be based on C-QTc modeling of the relationship between plasma concentrations of setmelanotide (or placebo) and $\Delta QTcF$ (using Day -1 time-matched Holter ECGs as baseline) with the intent to exclude an effect of $\Delta\Delta QTcF > 10$ msec at clinically relevant plasma levels, using the concepts presented in the “Scientific White Paper on C-QTc modeling” (Garnett 2018b, Garnett 2018a). After development of the C-QTc model and assessment of model performance through nonparametric bootstrapping, the $\Delta\Delta QTcF$ associated with the Cmax of therapeutic and supratherapeutic doses will be computed using bias-corrected 90% CI. An increase in QTc of ≥ 10 msec can be ruled out if the upper 90% CI is < 10 msec.

The change from baseline (Δ) and placebo-corrected change from baseline ($\Delta\Delta$) QTcF, HR, PR, and QRS will be summarized by nominal time and treatment using descriptive statistics. An analysis of categorical outliers will be performed for changes in QTcF, HR, PR, and QRS, and T-wave morphology, and U-wave presence and results will be summarized.

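### Table 4-2 flags heart-rate rises above 25% but has no row for falls, so slowing of more than 25% that stays at or above 40 bpm is left out of the heart-rate outlier count (minor)

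*SAP*

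**What the plan says.** SAP 3.2 introduces the derivations with "Changes from baseline and percent changes from baseline will be computed as". The percent change it then gives is 100 times the on-treatment value minus the time-matched Day -1 value, divided by the Day -1 value. No absolute value is taken, so a fall is negative.

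SAP 4.10.3.2.1 counts subjects, by day and treatment group, who meet at least one treatment-emergent criterion in Table 4-2. Three rows concern HR:

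- actual value below 40 bpm (flag L)
- actual value above 120 bpm (flag H)
- "HR relative change >25" per cent (flag I)

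The legend reads "I: Noticeable increase from baseline". There is no flag for a decrease.

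The endpoint served is wider than a rise. SAP 3.2.2 lists both HR and relative change in HR among the categorical outliers and gives no direction. Protocol 5.2.2 lists HR outliers without a direction. Protocol 11.3.1 says "An analysis of categorical outliers will be performed for changes in QTcF, HR, PR, and QRS", again with none.

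**The concern.** For PR and QRS, Table 4-2 tests only the upward direction, both in its actual-value rows and in its change rows, so for those two it is consistent. HR is different. It is the only one of the three with a lower actual-value limit, so the table already treats slowing as abnormal, but the change rows do not carry this through.

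At stake is what a named secondary endpoint counts. A subject with a large relative fall that stops at or above 40 bpm is absent from the incidence table, while a subject whose HR rises by the same percentage is in it. A reader of the finished table could take few entries in the HR-change row to mean few large HR changes in either direction. If slowing were then seen elsewhere, the threshold for counting affected subjects would have to be chosen after the data were known.

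**Working it through.** The plan states no figure for this point, so there is none to reproduce. The check has two parts: arithmetic on the table's own rules, then an illustration under assumed values.

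**1. Where the gap lies**

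Inputs: the signed formula (SAP 3.2), the three HR rows (Table 4-2), and the entry pulse limits as a stand-in for Day -1 HR (Protocol 6.2: "Subject has supine pulse rate of <45 beats per minute (bpm) or >100 bpm").

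- A fall of exactly 25% from baseline b leaves 0.75 × b. This is still at or above 40 when b ≥ 40 / 0.75 = 53.3 bpm.
- For whole-number baselines of 45 to 53 bpm, any fall of more than 25% ends below 40 and gets flag L. There is no gap there.
- For baselines of 54 to 100 bpm, a fall of more than 25% can end at or above 40. That is 100 − 54 + 1 = 47 of the 100 − 45 + 1 = 56 whole-number baselines.

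Examples that meet no row:

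| Day -1 (bpm) | On treatment (bpm) | Relative change |
|---|---|---|
| 60 | 42 | (42 − 60)/60 = −30.0% |
| 70 | 50 | (50 − 70)/70 = −28.6% |
| 80 | 55 | (55 − 80)/80 = −31.3% |

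The largest fall that gets no flag is the one ending at exactly 40 bpm: 25.9% from 54, 33.3% from 60, 42.9% from 70, 50.0% from 80 and 60.0% from 100. From each of these baselines, a rise just above 25% gets flag I.

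**2. How many subjects this could be**

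The documents give no HR level, variability or expected HR effect. Assumed instead: subject mean HR normal with mean 60, 65 or 70 bpm and SD 8, clipped to 46 to 100; 16 time-matched post-dose points; independent SD of 3 or 4 bpm per averaged point on each day; values rounded to integers as SAP 3.2 requires. A subject is uncounted if at least one point falls by more than 25% and no point is below 40 bpm.

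| Uniform shift | Any fall above 25% | Any HR below 40 | Uncounted |
|---|---|---|---|
| none | at most about 4% | – | – |
| −5 bpm | – | – | about 2% to 22% |
| −10 bpm | 36% to 87% | 3% to 34% | about 33% to 61% |

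Ranges run across the assumed means and SDs, and simulation error can move an end by about a point. For comparison, a uniform rise of 10 bpm would put 59% to 95% of subjects in the existing increase row.

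**The case against.** The strongest reply is that slowing would not escape the analysis.

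- SAP 4.2.5 requires the minimum and maximum of raw and change values for the ECG parameters by group, day and time point, and lists all recorded and derived ECG data by subject.
- SAP 4.10.3.1 estimates the placebo-corrected change in HR at every time point, by day, with 90% confidence intervals. With 20 versus 20 subjects and the SDs assumed above, the SD of a change is √2 × 3 = 4.2 to √2 × 4 = 5.7 bpm. The half-width is 1.686 × SD × √(2/20), or about 2.3 to 3.0 bpm. A uniform 10 bpm fall would be plain.
- SAP 4.11.6 lists individual hourly mean HR with time-matched changes.

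All of this stands. What is missing is one count of subjects, not the means to see slowing. But none of these outputs counts subjects beyond a relative fall, and that is what an outlier table adds to the means.

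The flags are also descriptive: the SAP says they need not reflect clinically significant events, and no test or decision rests on them. That stands too, and it limits the weight of the point.

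A reader might infer more than the documents support:

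- *That the QTcF analysis is at risk.* SAP 4.10.2.1.1 and 4.10.2.1.2 check the correction with plots of QTc change against HR change and provide an individual correction if there is a chronotropic effect. Neither step uses Table 4-2.
- *That the protocol names HR as the main cardiac concern of this trial.* The phrase "primarily because of the potential concern for effects on blood pressure (BP) and heart rate (HR" in Protocol 3.1.2 explains why nonclinical studies were done, and it names blood pressure as well.
- *That the 40 bpm limit is wrong because entry allows 45 bpm.* The upper limit of 120 bpm lies outside the entry limit of 100 bpm in the same way, so this is no defect.
- *That protocol and SAP contradict each other.* The protocol gives no thresholds and leaves technical detail to the SAP (Protocol 11.3).

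**Conclusion.** The gap is real and minor. That Table 4-2 cannot count an HR fall of more than 25% that stays at or above 40 bpm follows from the signed formula and the legend, and needs no assumption. That it can arise for 47 of 56 whole-number baselines rests on taking the entry pulse range for Day -1 Holter HR, which may fall outside that range at night.

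The share of subjects affected depends on assumed values: about 2% to 22% for a uniform 5 bpm fall and about 33% to 61% for 10 bpm. Nothing in the documents suggests that either fall will occur. Nor would the outlier table necessarily be near empty under slowing: with a 10 bpm fall, up to 34% of subjects would still reach the row for HR below 40.

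The primary decision rule (SAP 4.10.2.1.7), the assay-sensitivity rule (SAP 4.10.3.3) and the QT-correction checks are unaffected. The consequence is confined to one descriptive secondary endpoint, whose HR-change count is one-sided where the endpoint as worded is not.

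**What to change.** In SAP Table 4-2, under the changes from baseline:

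1. Add the row **HR relative change < −25%** with its own flag, for example D for a noticeable decrease, and add that flag to the legend.
2. Count it by day and treatment group in the same incidence table as the other rows.
3. Relabel the existing row **HR relative change > +25%**, so that its direction is explicit.

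Leave the other rows as they are. The change mirrors the plan's own 25% threshold and uses values already derived under SAP 3.2. It needs no new data and alters no model or decision rule. The downside is a few chance flags: at most about 4% of subjects with no drug effect, under the assumptions above.
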